9.2 SAMPLE SIZE DETERMINATION

The primary analyses will compare the difference in neural activity at individual electrodes depending on behavioral or computational regressors or classifications. Based on previous studies, we expect sample sizes of 10-20 patients to be sufficient to examine activation in individual brain regions of interest. With an estimated average of 2-4 iEEG electrodes per region per patient, this will result in sample sizes of 20-80 electrodes. Given that prior studies show only a subset of electrodes is active in response to specific conditions of regressors, with activation rates ranging between 5-30%, a difference of $10 \mu\text{V}^2/\text{Hz}$ in power activation in a specific frequency band (e.g. high gamma), this sample size will have $>90\%$ power to detect this difference using a two-sided test at $\alpha=0.05$.

Conversely, the main outcome measure for stimulation experiments will often be behavioral parameters, i.e. risk attitudes during decision-making tasks. Assuming a difference of 10 points in risk preferences (in line with prior results) scores, this sample size will have $>85\%$ power to detect this difference using a two-sided test at $\alpha=0.05$.

9.3 POPULATIONS FOR ANALYSES

There is no patient segmentation, and all patients that complete a specific behavioral task will be included in analyses.

9.4 STATISTICAL ANALYSES

9.4.1 GENERAL APPROACH

To identify association between behavioral and neural metrics, we will use a regression approach where the dependent variable was defined as the analytic amplitude of the neural time series. For trial-based analyses, the neural time series is subsequently divided into event-related epochs, normally averaging neural activity using a rolling window at (e.g. 200ms width, with 50ms increments). To identify task-selective channels, we performed separate linear regressions of average neural activity on each behavioral regressor of interest. Given the inter-trial variability in response latencies, this analysis may be performed separately time-locked to each behavioral event of

interest (i.e. task presentation, patient response). We use the resulting R^2 (variance in the neural data that can be explained by the behavioral regressors of interest, % explained variance, %EV) as a metric of the quality of the fit. This approach is insensitive with respect to time of task-related activation and to the direction of encoding (i.e., increases or decreases in neural activity). Electrodes will be classified as task active for any given regressor if they show a significant correlation ($p < 0.05$) at 5 or more consecutive time windows at any point during the epochs. False positive rate will be determined using a permutation strategy. For each regression, we will shuffle the relationship between behavioral labels and neural activity 1,000 times, and take the resulting distribution as the null for that particular regressor-electrode combination. In the case of single neuron analyses or voltammetry recordings, we will use the spiking activity or recorded neurotransmitter concentration as the variable of interest in a similar fashion.

In the case of multiple regressors of interest, we will verify that the encoding profile of individual electrodes is not affected by regressor collinearity, for example by using a stepwise regression model. In summary, the analysis for each electrode proceeded as follows: first, we will carry out multiple individual linear regressions for all regressors. To leverage the time profile of the signals without imposing restrictions on activation timing, an aggregate statistic was calculated as the sum of F-stats for the longest stretch of consecutive significant (linear regression $p < 0.05$) windows. We will repeat this procedure 10,000 times after shuffling the behavioral labels, and take the proportion of permuted fits with a sum-of-F-stat higher than that in the original dataset was taken as the permutation p value. This p value will be further corrected for multiple comparisons using a Bonferroni correction (across n electrodes); regressors that did not survive multiple comparisons will be considered not active. Subsequently, we will seek to identify the set of regressors that best explain neural activity variance by performing a model selection procedure on the surviving regressor set. We will first select the regressor that explains the most variance in the neural data (maximum peak %EV) as the base model, then create an alternative complex model by incorporating the second regressor that most improved the model. These two models will be compared using an ANOVA test; if the complex model results in a significantly improved fit (ANOVA $p < 0.05$), we will reject the basic model. This process will be iteratively repeated by adding new regressors, sorted by residual %EV improvement, until the model cannot be further improved (ANOVA $p > 0.05$). Finally, we will estimate the proportion of electrodes encoding each variable across all electrodes, regardless of the order in which they were incorporated into the model. To verify that the results were not driven by inter-subject or inter-electrode variability, we may conduct mixed-effects model analysis using the concatenated HFA for all electrodes as dependent variable, round-by-round regressors of interest (risk, regret, etc.) as fixed effects, and patient and electrode ID as nested mixed-effects.

In the case of behavioral analyses (i.e. for secondary endpoints), behavioral metrics or latent model parameters will be estimated from the behavioral data. To compensate for potential variability across patient behavioral strategies and behavior, we will whenever possible employ a within-subject analysis by completing a baseline behavioral task pre-stimulation (either before or during hospital admission). If possible, we will also test for lingering behavioral effects by carrying out behavioral testing post-stimulation.

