9.4.6 BASELINE DESCRIPTIVE STATISTICS

For all analyses, we will keep track of the patients' demographic information (age, sex, handedness, neuropsychiatric test results) and include these as covariates in analyses as necessary.

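### The single-electrode regressions leave out the trial's own pre-trial amplitude, so some encoding electrodes may be missed; how many depends on a correlation the plan does not give

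*Combined protocol and SAP*

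**What the plan says.** Section 9.2 sets the unit of the primary analysis: "The primary analyses will compare the difference in neural activity at individual electrodes depending on behavioral or computational regressors or classifications". Section 9.4.1 then says that "the dependent variable was defined as the analytic amplitude of the neural time series", that for trial-based work the series is "divided into event-related epochs, normally averaging neural activity using a rolling window at (e.g. 200ms width, with 50ms increments" and so on, and that "we performed separate linear regressions of average neural activity on each behavioral regressor of interest". On alignment it adds that "this analysis may be performed separately time-locked to each behavioral event of" interest. An electrode counts as task active if p<0.05 "at 5 or more consecutive time windows at any point during the epochs".

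The later part of 9.4.1 sums F over the longest significant run, compares that sum with 10,000 label shuffles, applies Bonferroni across electrodes, and then builds a stepwise model. The stepwise model ranks the surviving regressors by explained variance and compares nested fits. Only further behavioural regressors are added. A pooled check is optional: "we may conduct mixed-effects model analysis using the concatenated HFA for all electrodes as dependent variable", with patient and electrode identity as the grouping terms.

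Section 9.4.2 covers filtering, re-referencing and artifact removal, and names no use of pre-event activity. Section 9.4.6 lists patient-level characteristics and says the team will "include these as covariates in analyses as necessary". The only baseline in the plan is behavioural, for the stimulation endpoint (9.4.1 and 9.4.3).

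**The concern.** Amplitude on an electrode can drift between trials for reasons unrelated to the task. If a regressor is first revealed at or after trial onset, amplitude before the trial cannot depend on it, so pre-trial amplitude is a legitimate covariate that can only explain noise. Leaving it out keeps the shared variation in the error term of every window regression. That lowers F, shortens significant runs, and can push a true encoding electrode below the five-window rule or the Bonferroni-corrected sum-of-F threshold. The share of electrodes reported as encoding each variable would then be too low.

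Nothing else in the plan fills the gap. The 9.4.6 covariates are essentially constant within a patient and cannot reduce error within one electrode. The high-pass filter in 9.4.2 acts on voltage, and does not remove slow variation in the 70–200 Hz amplitude envelope.

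**Working it through.** **1. The plan's own power figure.** Section 9.2 states more than 90% power for a difference of 10 µV²/Hz with 20–80 electrodes, two-sided alpha 0.05. It gives no SD, so the figure can be neither reproduced nor refuted.

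- One-sample or paired test (noncentral t): 90% power needs SD ≤ 13.1 at n=20 and ≤ 27.3 at n=80.
- Two equal groups totalling N (normal approximation): SD ≤ 10 / [(1.960+1.282) × √(4/N)], which is 6.9 at N=20 and 13.8 at N=80.

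This figure counts electrodes. The regressions here count trials within one electrode, so 90% is not a starting point for what follows.

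**2. Analytic gain.** Inputs: rho is assumed (0.1 to 0.7), and so is a starting power of 80% at alpha 0.05. A covariate independent of the regressor multiplies residual variance by 1−rho², so adjusted power = Φ[(0.842+1.960)/√(1−rho²) − 1.960].

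| rho | √(1−rho²) | adjusted power |
|---|---|---|
| 0.1 | 0.995 | 80.4% |
| 0.3 | 0.954 | 83.6% |
| 0.5 | 0.866 | 89.9% |
| 0.7 | 0.714 | 97.5% |

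If rho has decayed from 0.5 to an assumed 0.18 late in the epoch, √(1−0.18²)=0.984 and power is only about 81%. At the Bonferroni level for 80 electrodes (0.05/80), an electrode with an assumed 50% power goes to about 50.6%, 56.5% and 70% at rho 0.1, 0.3 and 0.5.

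**3. Simulation of the sum-of-F statistic.** Assumed: 150 trials, 25 windows, effect 0.25 SD over 8 windows; 300 runs, 400 permutations, Monte Carlo SE up to about 3 points. Detection at permutation p≤0.005 (about Bonferroni for 10 electrodes):

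| rho | no baseline | covariate |
|---|---|---|
| 0 | 79.3% | 79.7% |
| 0.1 | 74.7% | 77.7% |
| 0.3 | 66.0% | 74.0% |
| 0.5 | 53.3% | 75.0% |

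A separate simulation, also with an assumed 150 trials, at p≤0.01 gave 69% vs 68% (rho 0), 67% vs 74% (0.3) and 53% vs 80% (0.5). With correlation decaying over the epoch it gave 63% vs 72%.

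**4. False positives.** Null rejection at p<0.05 in the 300-run simulation was 4.0–5.7% without the covariate and 4.7–7.7% with it. The SE is √(0.05×0.95/300) ≈ 1.3 points, so the top value is about two SEs above 5%. The separate simulation showed no excess. If labels are exchangeable and independent of baseline and outcome under the null, shuffling only the label is valid with or without the covariate.

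**5. Covariate or subtraction.** With equal variances, subtraction multiplies residual variance by 2(1−rho): 1.4 at rho 0.3 and 1.0 at rho 0.5, against 0.91 and 0.75 for the covariate. In the 300-run simulation at p<0.05, subtraction cut detection from 93.7% to 50.0% at rho 0 and from 89.7% to 72.0% at rho 0.3. It helped only from about rho 0.5 (86.3% to 90.0%).

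**6. Pooled check.** If electrodes enter in unequal units and share one standardised effect (both assumed), efficiency is 1/(1+CV²) of electrode scale: 1/1.25 = 80% at an assumed CV of 0.5, and 1/2 = 50% at CV 1.

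**The case against.** The best counter-argument is that the planned analysis is valid as written and that the benefit of adjusting is unknown. Both statements are true. The unadjusted permutation test holds its level. The documents give no rho, trial count or within-electrode SD. At rho 0.1 the analytic gain is under one point, and it shrinks where correlation fades, most of all in response-locked epochs far from the pre-trial window. The protocol also spans many tasks and keeps its methods deliberately flexible.

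Several stronger readings might be inferred, and the documents do not support them:

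- That the plan analyses raw, strictly post-event activity in native units. Epoch limits are not defined, and the text is silent on scaling.
- That the 90% in 9.2 would rise by a stated amount. It concerns electrode counts, not trials.
- That failing to normalise each electrode harms the primary tests. Rescaling an electrode by its own overall mean and SD leaves F, p and R² unchanged within that electrode.

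The objection also shows that a bare extra column is not enough. The stepwise step in 9.4.1 ranks regressors by explained variance and compares nested models, which fails if candidates have different base models. And for regressors carried over from earlier trials, pre-trial activity may itself be the signal, so adjusting could remove it.

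What remains is an unused covariate that is already recorded, cost nothing measurable in simulation when rho was zero, and helps at moderate rho.

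**Conclusion.** The omission is real, and no other section repairs it. It is a possible loss of power, not a validity flaw. A reader might infer that encoding electrodes are in fact being missed; the documents show only that some may be, because rho is not given.

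From an assumed 80% power at alpha 0.05, the gain is negligible at rho 0.1, about 4 points at 0.3 and about 10 points at 0.5. It is smaller if the correlation decays over the epoch, and was larger in the simulations of the sum-of-F statistic at stricter thresholds. These figures rest on assumed rho, trial counts, effect sizes and window layout, and on regressors independent of pre-trial amplitude. The change is worth making because it is cheap. The scaling point in the mixed-effects check is secondary, since that check is optional and the plan does not say how amplitude is scaled.

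**What to change.** In 9.4.1:

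- Sort regressors into those first revealed at or after trial onset and those known before the trial (for example, the previous outcome).
- For the first set, add the trial's mean amplitude in one fixed pre-trial window as a covariate in every window regression, not by subtraction. Use the same window for presentation- and response-locked epochs, ending before the event by at least the filter's smoothing length.
- Keep the covariate in the permuted fits and shuffle only the behavioural label.
- Define explained variance as partial R² given the covariate, and use the same base model, including it, for all candidates compared on an electrode in the stepwise selection.
- Keep the unadjusted model for regressors known before the trial, and analyse them as a separate set.
- Report the observed correlation between pre-trial and analysed amplitude.
- If the mixed-effects check is run, standardise each electrode's high-frequency amplitude before concatenation, so that high-amplitude contacts do not dominate. Grouping terms that act only as intercepts shift level but do not rescale.

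Cost: SAP wording, modest script changes, one degree of freedom per fit, a pre-trial window fixed in advance, and two regressor sets to maintain. No new data or patient burden.

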9.4.2 ANALYSIS OF THE PRIMARY ENDPOINT(S)

The main goal of the study is to understand the neurophysiological basis of human cognition. This will require integrated analysis of clinical, neurophysiological, anatomical, video and behavioral datasets.

Analysis of Electrophysiological Data: Some of the analysis will be performed at Mount Sinai, and some will be performed at collaborating sites. Any data sent to other sites will be de-identified. Typically, iEEG recordings are amplified x10000, analog filtered (0.01-1000 Hz) with $> 1\text{kHz}$ digitization rate, re-referenced to a common average or bipolar reference scheme offline and high-pass filtered at 0.1-1 Hz with a symmetrical (phase true) finite impulse response (FIR) filter (35 dB/octave roll-off). Channels with a low signal-to-noise ratio (SNR) are identified and deleted

(i.e., 60 Hz line interference, electromagnetic equipment noise, amplifier saturation, poor contact with cortical surface). Additionally, channels are visually inspected by a neurologist or research team member to exclude epochs of aberrant or noisy activity (typically < 1% of data points). A photodiode recorded screen updates in the behavioral task, recorded in the electrophysiological system as an analog input and used to synchronize behavioral and electrophysiological data. In some cases, different synchronization (through an audio feed into an analog channel or through TTL pulses) may be carried out. Data analysis is carried out in MATLAB and R using custom scripts and electrophysiological analysis toolboxes (e.g. Fieldtrip). Data for each channel is down sampled to 1KHz and filtered into high-frequency activity (HFA; 70–200 Hz) using a two-way, zero phase-lag, finite impulse response band pass filter to prevent phase distortion. Alternatively, time-frequency representations are created using wavelets, or equivalent methods, using linearly or logarithmically spaced frequencies, which allows for comparisons between time-varying high-frequency and low-frequency signals on an equal footing. This is especially important for iEEG signals, which are generally nonstationary and have time-varying phase components. We will also measure coherence and phase synchronization to quantify the degree to which oscillatory effects are synchronized across brain regions.

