9.4.3 ANALYSIS OF THE SECONDARY ENDPOINT(S)

The secondary endpoints will involve analysis of behavioral modulation resulting from electrical modulation of neuronal activity. As such, they will be task specific, but in most instances this will entail estimation of a behavioral (for example, proportion of remembered items in a memory task) or computational (derived from behavior through the application of computational models) metric of interest in pre-stimulation (baseline) and stimulation conditions. We will carry out within-patient comparisons to account for inter-patient variability, and in most instances will carry out two-tailed statistical tests (e.g. two-tailed t-test) to compare individual behavioral/computational estimates.

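### Freely shuffling trial labels gives permutation p-values that are too small when both the task regressor and the neural amplitude are serially dependent

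*Combined protocol and SAP*

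**What the plan says.** Section 9.4.1 regresses windowed neural activity on one behavioural regressor at a time. An electrode counts as task active if it shows a "significant correlation ($p < 0.05$) at 5 or more consecutive time windows". The null for each regressor-electrode pair comes from a shuffle: "we will shuffle the relationship between behavioral labels and neural activity 1,000 times".

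The same section then summarises each electrode by the "sum of F-stats for the longest stretch of consecutive significant (linear regression $p < 0.05$) windows" and obtains its p-value by permutation: "We will repeat this procedure 10,000 times after shuffling the behavioral labels". That p-value is Bonferroni-corrected across electrodes. Regressors that survive go into model selection, and the share of electrodes encoding each variable is then reported. The approach is extended to single-neuron and voltammetry data.

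Section 9.4.2 describes a further procedure that swaps items at random between categories, using one randomisation for all electrodes.

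None of these texts limits the shuffle to blocks, runs or neighbouring trials. No trial-order covariate, detrending or autocorrelation term is named. The plan describes "round-by-round regressors of interest (risk, regret, etc.) as fixed effects" in an optional mixed model, and Section 9.2 refers to regressors that may be behavioural or computational.

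**The concern.** Shuffling labels treats every ordering of trials as equally likely under the null. That is harmless if the regressor is drawn afresh on every trial, or if neural activity is exchangeable over trials. It fails when both series move slowly, because two unrelated slow series often correlate by chance. The shuffle destroys the slow structure, so its null is too narrow.

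Both conditions are plausible for some tasks here. Section 4.1 describes sessions of 60-90 minutes and tasks made up of successive choices with uncertain outcomes. A regressor computed from past outcomes carries over by construction: a running average m(t) = (1-w)m(t-1) + w·outcome(t) with independent outcomes has lag-1 correlation 1-w, which is 0.5 at w = 0.5 and 0.8 at w = 0.2 (illustrative weights).

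The p-value decides which electrodes and regressors are called active. Section 9.2 expects 5-30% of electrodes to be active, and false-positive rates of the size shown below fall within or above that range. Artefact and finding could then look alike.

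**Working it through.** The plan gives no false-positive rate of its own to reproduce.

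**From the documents:** free label shuffles, the sum-of-F statistic, window p < 0.05, 200 ms windows in 50 ms steps (9.4.1); two-sided alpha 0.05 and 20-80 electrodes (9.2).

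**Assumed, because the documents are silent:** 100 or 200 trials; a 2 s epoch, giving (2000-200)/50 + 1 = 37 windows; neural data made of independent noise plus a trial-to-trial AR(1) drift carrying share s = 20% of variance; an unrelated AR(1) regressor.

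**Formula for a single correlation.** With lag-1 correlations a (regressor) and b (drift), the variance of the correlation is inflated by V = 1 + 2s·ab/(1-ab). The true error at nominal 5% is 2[1-Φ(1.96/√V)].
- 0.5 and 0.5: V = 1 + 0.4×0.25/0.75 = 1.133; 1.96/1.065 = 1.84; error 6.6%.
- 0.8 and 0.8: V = 1 + 0.4×0.64/0.36 = 1.711; 1.96/1.308 = 1.50; error 13.4%.

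**Simulation of the planned sum-of-F statistic** under a true null (1,000 simulated electrodes per cell, 1,000 shuffles; Monte Carlo standard error about 0.7 points at 5%):

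| Lag-1, regressor / drift | Formula | 100 trials | 200 trials |
|---|---|---|---|
| 0 / 0, no drift | 5.0% | 4.9% | 5.0% |
| 0 / 0.95 | 5.0% | 4.6% | 5.2% |
| 0.95 / 0 | 5.0% | 4.5% | 5.9% |
| 0.5 / 0.5 | 6.6% | 8.5% | 7.2% |
| 0.8 / 0.8 | 13.4% | 18.5% | 22.6% |
| 0.95 / 0.95 | 36.6% | 39.7% | 43.0% |

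The level holds when only one series is dependent. At 0.95 the result depends on the drift share: 5% drift gives 17% (100 trials) or 25% (200), and 40% drift gives 51% or 57%.

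**Bonferroni.** With 20 electrodes the per-test level is 0.05/20 = 0.0025. At 200 trials the per-electrode error is 6.3% at 0.8 and 24.6% at 0.95, which is 0.063/0.0025 = 25 and 0.246/0.0025 = 98 times nominal. Exchangeable trials gave 0.1-0.7%.

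**Five-window rule.** With drift at 0.95 and an independent regressor it fires in 1.5% (100 trials) or 3.2% (200) of null electrodes. With the regressor also at 0.95 it fires in 33% or 38%.

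**Other safeguards.**
- The shared randomisation in 9.4.2 handles dependence between electrodes, not between trials.
- The covariates in 9.4.6 are patient-level.
- The mixed model is optional and has only patient and electrode effects.
- The 0.1-1 Hz high-pass acts on voltage before the 70-200 Hz amplitude is extracted, so slow drift of that amplitude remains.

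**Alternative nulls (200 trials, 20% drift).** Redrawing the regressor from its own serial process gave 5.0%, 5.8% and 4.0% at 0.8, 0.9 and 0.95; free shuffling gave 21%, 36% and 44% in the same comparison (500 shuffles). In a separate check with a simpler statistic, free shuffling gave 7.2% and 12.7% at 0.5 and 0.8. Phase-randomised surrogates plus trial number gave 5.3% and 4.9%, and also held at the 0.0025 level.

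**The case against.** The strongest reply is that the documents establish neither condition. They report no serial correlation in any regressor, no drift size and no trial count. If rounds are drawn independently, the planned shuffle is valid even with drift. The text also never says that the shuffle is unrestricted. All of this stands, and it makes the point conditional and task-specific. It does not remove it: one rule covers every task, no restriction is stated, and nothing tells the analyst when free shuffling is justified.

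Four stronger readings are tempting and are not supported.
- A reader might take "iEEG signals, which are generally nonstationary and have time-varying phase components" as an admission that amplitude drifts across trials. In 9.4.2 that phrase justifies time-frequency methods; it does not describe drift over a session.
- A reader might take "computational (derived from behavior through the application of computational models) metric of interest" as evidence that the electrode regressors are model-derived. In 9.4.3 it concerns the secondary behavioural endpoint.
- A reader might infer 12.9% and 36% error at lag-1 correlations of 0.5 and 0.8. Those follow from V = (1+ab)/(1-ab), which gives the whole neural measure the drift's autocorrelation and leaves no independent trial noise. With a 20% drift share the same approach gives 6.6% and 13.4%. Likewise, family-wise error over 80 electrodes (independence assumed) falls from 48% and about 100% to 10% and 51%.
- A reader might call the permutation the plan's only Type I error control. The consecutive-window rule and Bonferroni are also there, although neither addresses dependence between trials.

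**Conclusion.** The concern holds conditionally. As written, the shuffles in 9.4.1 and 9.4.2 give p-values that are too small whenever the regressor and the single-trial neural measure are both serially dependent. With 200 trials and 20% drift variance, error at nominal 5% is about 7% at lag-1 correlation 0.5, 13-23% at 0.8 (lower for a single correlation, higher for the planned sum-of-F), and about 40% at 0.95. These sizes rest on assumed trial count, drift share and autocorrelation. They show what could happen and do not estimate the error rate of any task in this study. For a regressor randomised independently on each trial the error stays at 5% and nothing needs to change.

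**What to change.** In 9.4.1 and 9.4.2, state for each task which null applies.

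- Regressors independently randomised on every trial: keep free shuffling.
- All other regressors: add trial number as a nuisance term and build the null from surrogates that keep the regressor's serial structure. For continuous regressors, redraw the series from the task or fitted model, or use phase-randomised surrogates. For categorical labels, which phase randomisation does not preserve, redraw the task sequence or permute within runs.
- Use the same surrogate for all electrodes within a patient. It cannot be shared across patients whose behaviour differs.
- Use block permutation only where the number of distinct orderings can resolve the Bonferroni threshold. With 100 trials in blocks of 20 there are 5! = 120 orderings, so the smallest p-value is 1/120 = 0.008, above 0.0025. Circular shifts have a similar limit: 200 trials allow at most 199.

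The trial-number term matters. With linear trends in both series (20% of regressor and 10% of neural variance, 200 trials, simple correlation), phase surrogates alone still gave 28% error and blocks 38%, against 51% for free shuffling. Activity should also be called from the surrogate p-value, because changing the null does not alter how often the raw five-window rule fires.

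The cost is SAP wording, a little more code, and somewhat larger p-values for slowly varying regressors, hence some loss of power. Coarse blocks lose power even when trials are independent: at 200 trials and per-test level 0.000625, power for a simulated effect fell from 93% to 86%. No new data or patient procedures are needed.

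### The forward selection meant to guard against collinearity uses an unadjusted p < 0.05 and does not fix the time window; if the window is searched, correlates are counted as encoded far more often than 5%

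*Combined protocol and SAP*

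**What the plan says.** Section 9.4.1 gives the purpose of the step: "we will verify that the encoding profile of individual electrodes is not affected by regressor collinearity, for example by using a stepwise regression model". The procedure has three stages.

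1. **Screen.** "first, we will carry out multiple individual linear regressions for all regressors". Each regressor gets a permutation p-value from a run statistic over time windows, Bonferroni-corrected across electrodes.
2. **Selection among the survivors.** "We will first select the regressor that explains the most variance in the neural data (maximum peak %EV) as the base model". The analysts will "then create an alternative complex model by incorporating the second regressor that most improved the model", and the addition is judged as follows: "if the complex model results in a significantly improved fit (ANOVA $p < 0.05$), we will reject the basic model". After that, "This process will be iteratively repeated by adding new regressors, sorted by residual %EV improvement, until the model cannot be further improved".
3. **Count.** For each variable, the plan reports the share of electrodes whose final model contains it, whatever the order of entry.

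The windows come from "normally averaging neural activity using a rolling window at (e.g. 200ms width, with 50ms increments" and so on. The epoch length, the number of regressors and the window used for the ANOVA and for the residual gain are not stated.

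**The concern.** The screen looks at one regressor at a time. A regressor that is only correlated with the truly encoded one really is associated with the signal, so it can pass, and correcting for the number of electrodes does not change that. Removing it is left to the selection stage.

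That stage uses an ordinary nested F-test at 0.05. The p-value is valid for one regressor and one window chosen beforehand. It is not valid at a window chosen because the gain was largest there, and the plan does not rule out that choice. At stake are the per-variable shares of encoding electrodes, which serve the primary objective.

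**Working it through.** **Inputs from Section 9.4.1.** Entry threshold 0.05 per step, no adjustment; windows of 200 ms at 50 ms steps (given as an example); base regressor chosen by its peak over windows.

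**Assumed inputs (not in the documents).**
- Simulation 1: 150 trials, 1.5 s epoch, 15% explained variance for the true regressor, correlates with r = 0.5 to 0.7 and no effect of their own, no screen. Windows: (1500 − 200)/50 + 1 = 27.
- Simulation 2: 200 trials, 2 s epoch, so (2000 − 200)/50 + 1 = 37 windows; screen at 0.05/60 (60 electrodes); 1, 3 or 5 pure correlates with r = 0.5 or 0.7; peak explained variance 15%, or 25% (run only with 3 correlates); 500 electrodes per setting.

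The plan states no error rate for the selection as a whole, so there is no figure to reproduce beyond the nominal 5%.

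**Test.** With S the regressors already in the model and j the candidate, F = (RSS_S − RSS_S+j) / (RSS_S+j / df), compared with the 95% point of F(1, df).

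**Benchmark.** One pre-specified correlate at one pre-specified window, with the true regressor in the model, was significant in 3.2% to 6.2% of simulated electrodes, consistent with 5%.

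**What passes the screen (simulation 2).** At 15% explained variance, about 40% of correlates with r = 0.5 and about 88% with r = 0.7 survive. At 25%, about 79% and nearly all survive.

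**Reading A: ANOVA at the base regressor's peak window.**
- Chance that any of m independent null candidates enters: 1 − 0.95^m, which is 9.8% for m = 2 and 18.5% for m = 4. Simulation 1 gives 9–10% and 17–19%.
- With the screen (simulation 2): 2.6–3.8% for 1 correlate, 6.2–14.6% for 3 and 11.8–19.6% for 5.
- Rate per variable, which is what the plan reports: 4.3–5.7% under simulation 1's inputs, whatever the number of candidates. Simulation 2 agrees. With 5 correlates and r = 0.7, 0.22 correlates were counted per electrode out of 4.37 surviving, and 0.22/4.37 = 5.0%.

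**Reading B: ANOVA at the window where the gain peaks.**
- Simulation 1, one candidate, independent 50 ms bins: 58–61% for r = 0.5 to 0.7.
- Same, r = 0.6, with autocorrelation between bins:

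| Bin autocorrelation | False addition |
|---|---|
| 0 | 60% |
| 0.5 | 48% |
| 0.8 | 35% |
| 0.9 | 27% |

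- Plausibility check for independent bins: a 1.5 s epoch holds 7 non-overlapping windows, and 1 − 0.95^7 = 30%. If all 27 windows were independent, 1 − 0.95^27 = 75%. The simulated 60% lies between.
- Simulation 2, screen included, chance that any correlate is counted: 32–63% for 1 correlate, 60–96% for 3 and 79–97% for 5. Per surviving correlate, with 1 correlate in play, this is 0.323/0.42 = 77% (r = 0.5) and 0.630/0.88 = 72% (r = 0.7). This grid is longer, and bin autocorrelation was not varied.

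**Effect on the reported share.** Section 9.2 expects 5–30% of electrodes to be active. With one correlate under reading B (32–63%, screen included), the share of all electrodes falsely labelled is 0.05 × 0.32 = 1.6% to 0.05 × 0.63 = 3.2% at the low end, and 0.30 × 0.32 = 9.6% to 0.30 × 0.63 = 18.9% at the high end. Under reading A the high end is at most about 0.30 × 0.05 = 1.5%.

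**The case against.** The strongest reply is that the plan never says the added regressors are tested at their best window. The peak is mentioned only for choosing the base. At a fixed window the nested F-test conditions on the base regressor and rejects about 95% of pure correlates. Choosing the best candidate first does not raise the rate per variable, because a null regressor normally still needs its own partial p below 0.05. This stands. Three stronger readings therefore lack support:

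- A reader might infer that the plan certainly searches windows at this step. The text is silent.
- A reader might infer from the 9–19% figures that the reported shares are inflated even at a fixed window. Those are chances that any of several candidates enters, and the plan sets no such rate for this stage.
- A reader might take risk and regret, named in the mixed model, as the collinear pair. The documents do not say that they are correlated.

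It can also be said that stepwise regression is offered only as an example and that the study is observational. However, the text then sets the steps out as the analysis for each electrode and names no alternative.

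The other safeguards do not reach this step. The label swapping in Section 9.4.2 addresses many electrodes and frequencies, and it tests for no association at all, not for no added association given the base. The mixed model is optional and is aimed at differences between subjects and electrodes.

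**Conclusion.** The concern holds conditionally. The entry test is unadjusted, its window is unspecified, and the plan's permutation and Bonferroni corrections stop at the screen. If the gain is taken at its peak over windows, a pure correlate that reaches the step is falsely counted in about 27–60% of cases (150 trials, 27 windows, 15% explained variance, r = 0.5 to 0.7, bin autocorrelation 0.9 down to 0), and more often on a longer grid. This reading is plausible: the base is chosen by its peak, and Section 9.4.1 aims not to restrict when activation may occur. If the window is fixed at the base regressor's peak, the rate per variable stays near 5%, and only the chance that some correlate enters rises.

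The sizes rest on assumed inputs; the upward direction under a window search does not. This should be fixed before analysis. It does not make the design unsound, because the error may be nominal if the window is fixed.

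**What to change.** 1. State the window at which the residual gain and the ANOVA are computed.
2. At each step, permute the residuals of the model already accepted. Record the maximum statistic over all remaining regressors and all windows searched, and take the entry p-value from that distribution. An alternative is to fit all regressors jointly in every window and test each one's unique contribution with the plan's run statistic and a Freedman-Lane permutation.
3. Count an electrode as encoding a variable only if that variable passes.

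In simulation 2, the residual permutation in step 2 (99 permutations) brought the chance of adding any correlate to 1.4–6.1% when the true regressor was the base, and to 1.4–8.6% overall. The excess comes from electrodes where a correlate was itself chosen as base (0–4.4%), which this change does not cure.

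The cost is SAP wording and computing time. The downside is that fewer electrodes will be labelled as encoding strongly collinear variables.
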